3.3 STUDY POPULATION

The study population comprises all patients with T2DM attending the Diabetes clinic at KATH. Participation in the study will be limited to individuals who meet the set criteria.

3.4 STUDY PERIOD

The study will take place from August 2023 to April 2024

3.5 STUDY FLOW DIAGRAM

Version 1 30 May 2023

3.6 SCREENING OF PARTICIPANTS

Individuals seeking care at the diabetes clinic will be approached by the principal investigator to introduce the study to them. They will be briefed on the study purpose and objectives and those who provide consent will be screened using the participant screening sheet (appendix A).

Following the screening procedure, persons who meet the inclusion criteria and provide consent for inclusion will have blood sample collected for measurement of baseline HbA1c using semi-automated Quo-Lab HbA1c analyser. Individuals with T2DM and baseline HbA1c $> 7.9\%$ will then be recruited into the study.

3.7 STUDY ARMS

3.7.1 USUAL CARE

The current standard practice (the usual care) includes an outpatient specialist service with patients scheduled every 1 to 6 months, depending on their diabetes control and complications profile. The other services provided include dietician appointments, laboratory investigations, clinical examinations, group education on self-management practices, and medication refills.

Usual care by a doctor entails a 10–15 min standard doctors' consultation where the recent HbA1c level and medication compliance are reviewed, and a brief informal patient-tailored diabetes education is offered. This enables the individual an opportunity to learn about self-management in a flexible and informal way. There is no structure to it and the information is offered according to what the patient requests to know as well as what the doctor thinks would be important for the patient to know, during that consultation.

Phone calls will be made to remind them of their clinic appointment for data collection.

[figure not shown]
3.7.2 DIABETES SELF-MANAGEMENT EDUCATION

The intervention group will receive the usual consultation from their doctor and referral to a trained diabetes educator for individualised structured DSME training. An empowerment and

interactive teaching model will be used with focus on behavioural assessment, goal-setting and problem-solving to promote autonomous self-regulation for better health and quality of life. A clinical sheet will be used while delivering the education to ensure that all core topics are covered.

For this study, 3 trained diabetes educators will offer the individualised DSME sessions using the American Association of Diabetes Education (AADE) 7 self-care behaviour model which focuses on: being active, healthy eating, monitoring blood glucose, healthy coping, reducing risks, problem solving and adherence to medication (19).

Version 1 30 May 2023

The participants are scheduled to attend a 30 minutes individualised session at the hospital every 3 months as well as telephone consultations lasting up to 15 minutes every 2 weeks at the convenience of the participant to reinforce DSME for 6 months. The first session is arranged on the first day of consultation with the doctor. At the end of the sessions, the participants will receive a patient guide to diabetes booklet and graphic material illustrating several self-care activities such as foot care. Subsequent consultations will be mainly feedback sessions, aimed at reviewing previously discussed matters, reinforcing key messages, addressing challenges and providing additional information.

The patients will also receive telephone reminders, a week prior to their scheduled appointment with the doctors, to ensure confirmation of their visit. A hotline number will be made available to them to consult with the diabetic educator at any given time of the day. Participants will be counselled that if FBG is less than 4.0mmol/L upon self-monitoring, they should take 15g of glucose(250mls of Coke, Spirite or Fanta drink) and call the hotline number provided.

Monthly meetings will be held with educators and research assistant to provide feedback on study progress and ensure quality control in the administration of intervention.

3.8 RANDOMISATION

The principal investigator will invite all the eligible patients for participation, and randomise them equally into two groups based on computer-generated random numbers and inform them of the assigned group. The randomisation allocation sequence will remain concealed from the doctors to further eliminate conscious or unconscious selection bias. After recruitment, the patients will complete their demographic and medical history information on a standard data collection form.

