3.2 STUDY DESIGN

This is a parallel-group, 2-arm randomized controlled trial among sub-optimally controlled ($\text{HbA1c} > 7.9\%$) T2DM patients to compare the effectiveness of a 6-month DSME intervention on glycaemic control in addition to usual diabetes care with usual care alone.

The minimum sample size of study participants will be determined using the formula (18)

$$n_i = 2 \left(\frac{Z_{1-\alpha/2} + Z_{1-\beta}}{ES} \right)^2$$

$$ES = \underline{\mu_1 - \mu_2}$$

$$\sigma$$

Where n_i is the sample size in each of the groups for a statistically significant study;

$\mu_1 - \mu_2$ is the absolute value of the difference in means (HbA1c) between the two groups expected under the alternate hypothesis which is 1.5% for this study;

σ = standard deviation of the outcome of interest which is 2.25 based on study by Asante et al(14)

ES is effect size which is calculated to 0.7

$1 - \beta$ is the power which is 80% for this study and $Z_{1-\beta}$ is the value from the standard normal deviation holding $1 - \beta$ below it.

α is the selected level of significance which is 0.05 for this study, $Z_{1-\alpha/2}$ is the value from the standard normal deviation holding $1 - \alpha/2$ below it. selected level of confidence set at 0.05 for this study

32 subjects in each group will be needed to ensure an adequate trial. An assumed 15% attrition and drop-out rate over the study period will be added to make a total sample size of 74 participants.

[figure not shown]

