3.10 DATA COLLECTION METHODS AND MEASUREMENTS

3.10.1 RECRUITMENT AND DATA COLLECTION FOR MEDICAL HISTORY

Following the screening and measurement of baseline HbA1c, individuals with T2DM and HbA1c >7.9% will be eligible for recruitment. All patients who give informed consent (appendix D) will be then entered into the study.

A structured questionnaire will be used to collect data on demographics, medical history including presence of other co-morbidities, drug history.

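### Concealment in section 3.8 is stated for the doctors but not for the principal investigator, who approaches, invites, randomises and informs the patients

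*Combined protocol and SAP*

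**What the plan says.** Three statements bear on who controls entry to the trial.

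- **Approach.** Section 3.6: "Individuals seeking care at the diabetes clinic will be approached by the principal investigator to introduce the study to them".
- **Invitation, randomisation and disclosure.** Section 3.8: "The principal investigator will invite all the eligible patients for participation, and randomise them equally into two groups based on computer-generated random numbers". The same sentence, with the same subject, ends "and inform them of the assigned group".
- **Concealment.** The next sentence of section 3.8: "The randomisation allocation sequence will remain concealed from the doctors to further eliminate conscious or unconscious selection bias".

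On entry, section 3.10.1 takes patients with T2DM and a baseline HbA1c above 7.9% and says: "All patients who give informed consent (appendix D) will be then entered into the study". Section 3.2 plans a "total sample size of 74 participants".

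The available text does not say who generates or holds the list, how an assignment is released, whether the list is simple or blocked, or whether entry is recorded before the assignment is known. The flow diagram (section 3.5) and the appendices cannot be seen here, so a mechanism described there cannot be excluded.

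**The concern.** Concealment prevents selection bias only if it covers whoever decides that a given patient enters at a given moment. In this protocol that is the principal investigator, yet the concealment sentence names a different group.

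If the enroller could know or predict the next assignment, the choice of whom to approach, and when, could differ by arm, even unconsciously. The intervention works through the patient's own self-management, so a difference in motivation between arms would bear directly on HbA1c at 6 months. Section 3.11.1 plans an unadjusted t-test. Even an analysis adjusted for measured baseline values would leave an imbalance in unmeasured motivation in place. The protection therefore has to be built in before enrolment.

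**Working it through.** **1. Roles side by side**

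| Step | Who, according to the text | Section |
|---|---|---|
| Approaches patients | Principal investigator | 3.6 |
| Invites eligible patients | Principal investigator | 3.8 |
| Randomises | Principal investigator | 3.8 |
| Tells patients their group | Principal investigator | 3.8 |
| Sequence concealed from | The doctors | 3.8 |
| Generates and holds the list | Not stated | – |
| Releases each assignment, and when | Not stated | – |

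**2. Who the doctors are.** Sections 3.7.1 and 3.7.2 use the word for the clinicians who run consultations; reminders, for example, go out "a week prior to their scheduled appointment with the doctors". No section gives them an enrolment task. There are two possible readings:

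- The doctors do not include the investigator. Concealment then covers people who do not enrol and omits the person who does.
- The doctors do include the investigator. The two sentences of section 3.8 then conflict unless there is an undescribed mechanism, because the person from whom the sequence is concealed is also the one who randomises.

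Section 3.8 needs correcting on either reading.

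**3. Why the list type matters.** The investigator tells patients their group and so knows past allocations. The protocol says only "randomise them equally into two groups", which does not show whether balance is forced. The table gives the expected number of the 74 assignments that are certain in advance. It assumes an enroller who knows past allocations and the list design, and counts the 2 patients left over after full blocks as 0.

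| List type (assumed) | Calculation | Certain in advance |
|---|---|---|
| Fixed blocks of 4 | 18 full blocks × 1.333 | 24.0 |
| Fixed blocks of 6 | 12 full blocks × 1.5 | 18.0 |
| Forced 37/37 total, no blocks | 2 × 37/38 | 1.95 |
| Simple randomisation | – | 0 |

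The values per block come from enumerating all 1:1 orderings. The protocol does not say which row applies.

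**4. What a bias would do, as illustration only.** Inputs from section 3.2: SD 2.25, 32 per arm. The bias of 0.25 HbA1c points is an arbitrary assumption.

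- SE = 2.25 × √(2/32) = 0.5625
- Noncentrality = 0.25/0.5625 = 0.444, with 62 df
- Two-sided rejection rate with no true effect = 0.072, against 0.050 without bias

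**5. Cost of simple randomisation.** With 74 patients, Binomial(74, 0.5) gives a 95% range of 29 to 45 per arm. Power by noncentral t for the planned difference of 1.5 with SD 2.25:

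- 37/37: SE = 2.25 × √(1/37 + 1/37) = 0.523; power 80.8%
- 45/29: SE = 2.25 × √(1/45 + 1/29) = 0.536; power 78.9%

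Both figures treat all 74 as analysed. At the planned 32 per arm after attrition, the same method gives 74.7%. The comparison therefore shows only the loss from imbalance, 80.8 − 78.9 = 1.9 percentage points; it does not give the trial's expected power.

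**The case against.** The strongest reply is that nothing in the text shows the list to be exposed. That is correct. A reader might infer from section 3.8 that the investigator sees the next assignment, or that allocation is already compromised. The documents do not support that: randomising from computer-generated numbers is compatible with a concealed release that is not described, and the flow diagram and appendices are unavailable.

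Discretion is also narrower than in many trials:

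- Section 3.8 has every eligible patient invited.
- A measured HbA1c decides eligibility, and section 3.6 takes consent before that sample.
- The budget lists 300 HbA1c tests. If 74 are for month 6 and none are repeats or spares (an assumption), 300 − 74 = 226 are for screening, and 74/226 is about one in three. An enroller who foresaw the next assignment could not be sure, on approaching a patient, that this patient would take it.

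These points weaken any steering but do not remove it. Section 3.1 reports about 40 attendances a day and only 74 patients are needed, so the choice of whom to approach first remains. Some criteria in sections 2.6 and 2.7 also call for judgement, such as mental stability, or anaemia with no threshold.

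The objection to the figures stands as well. The protocol mentions no blocks, the 0.25-point bias is not derived from anything in it, and neither figure measures this trial.

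**Conclusion.** The point holds as a gap in the stated safeguard. As written, section 3.8 directs concealment at people with no described enrolment role and does not extend it to the person who enrols, so its stated protection against selection bias does not reach the person who could influence entry. This goes beyond missing detail, because the rule that is stated names the wrong group or, on the inclusive reading, conflicts with the sentence before it.

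The size of any resulting bias is unknown. The predictability counts and the 7% type I error are illustrations under assumptions that the protocol does not make, and no estimate for this trial follows from them. The conclusion rests on the available text of sections 3.6 to 3.8 and 3.10.1. If an undisplayed figure or appendix describes a release mechanism, the remaining work is to bring it into section 3.8 and correct the sentence. The change should be made because it is cheap and later analysis cannot replace it. Confidence is medium.

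**What to change.** State in section 3.8:

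1. An existing team member with no part in recruitment generates and holds the 1:1 computer-generated list, and keeps the envelopes if any are used. The documents do not say whether the supervisors recruit, so this must be confirmed before one of them is named.
2. That person releases each assignment only after consent, eligibility including baseline HbA1c, and entry have been recorded against a participant ID. The demographic and history form need not be complete first; concealment does not require it.
3. The list uses simple randomisation, or randomly varying block sizes not disclosed to the enroller.
4. The sequence is concealed from the person enrolling participants and from the doctors.

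The cost is protocol wording, up to 74 envelopes or an equivalent release by the list holder, and minor organisation with existing staff. There may be a short wait for release at the first visit, since section 3.7.2 arranges the first education session on the first consultation day. Simple randomisation can leave unequal arms, with the small loss of power shown above; undisclosed varying blocks largely avoid this. Treatment, endpoint and sample size do not change.

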3.9 STUDY INSTRUMENTS

The following materials, equipment, and reagents will be used to obtain the data.

1. Consent form
2. Participant screening sheet
3. Structured Questionnaire
4. Clinical sheet

5. EDTA bottle container
6. Serum Separating Tube
7. Accu Chek Glucometer
8. Blood pressure monitor, weight scale and stadiometer
9. Measuring tape

3.10 DATA COLLECTION METHODS AND MEASUREMENTS

3.10.1 RECRUITMENT AND DATA COLLECTION FOR MEDICAL HISTORY

Following the screening and measurement of baseline HbA1c, individuals with T2DM and HbA1c >7.9% will be eligible for recruitment. All patients who give informed consent (appendix D) will be then entered into the study.

A structured questionnaire will be used to collect data on demographics, medical history including presence of other co-morbidities, drug history.

3.9.2 PHYSICAL MEASUREMENTS

Measurements will follow the WHO guidelines for physical measurements (20)

Weight measurement will be done using the Omron HN286 electronic human weighing scale. The participants will take off their shoes, empty their pockets and stand erect on the scale which will be placed on a firm flat floor and set to zero display. The weight will be recorded to one decimal place (20).

The height measurements will be done using the Seca 213 mobile stadiometer. This will be placed on a firm flat surface against the wall. Participants will stand on the board with their feet together, heels against the backboard, and their knees straight. With the participants looking straight ahead and their eyes at the same level as the ears, the height measurements will be read to the nearest 0.1cm with the measuring arm placed gently on the head. BMI will be calculated from the weight and height measurement using the formula: $BMI \text{ (kg/m}^2\text{)} = \text{weight (kg) /height}^2 \text{ (m}^2\text{)}$.

Waist circumference (WC) will be measured in the horizontal plane midpoint between the lower margin of the last palpable rib and the top of the iliac crest (hip bone) with a measuring tape with the participant's arms relaxed at the side and at the end of normal expiration. WC will be measured in a private room and recorded to the nearest 0.1cm. Blood pressure measurements will be done using a validated 'Omron M3 Intelli IT' Upper Arm Blood Pressure Monitor. Participants will sit quietly with their feet on the floor and their clothes loosened around the arm for at least five minutes before the blood pressure readings will be taken. A correct-sized cuff (bladder width being 80% of the arm circumference) will be placed on an exposed arm about 2 cm above the elbow, with the tube placed in front and at the centre of the arm. The blood pressure reading which will show some minutes after pressing the start button will be documented. Three measurements will be taken three minutes apart and the mean of the second and third readings will be used for the analysis.

3.9.3 BIOCHEMICAL ASSAY

Fasting blood glucose will be measured using Accu Chek Instant glucometer at the DM Clinic on every hospital visit.

Blood samples will be taken by trained laboratory technicians adhering to standard procedures including infection prevention and control practices. 10mls of venous blood will be obtained from each patient with 5ml each in an EDTA tube for HbA1c and serum separation test tube for lipid profile respectively taken at baseline and 6 months after recruitment. Each tube will be properly marked with unique identifiers and codes to de-personify the participants. All samples for lipid profile measurements will be kept in sample bags and sent to the biochemistry lab of the Komfo Anokye Teaching Hospital for processing. The samples will be processed and analysed with the Vitros® 5600 integrated immunochemistry analyser and a semi-automated Quo-Lab HbA1C analyser to determine the lipid profile and the HbA1c respectively.

3.9.4 DSME

A clinical sheet will be used by the diabetes educators while delivering the education to ensure that all core topics are covered

3.10 FOLLOW UP

Each study participant will be followed up for 6 months starting from the first encounter which is the first day of recruitment and ending at the last encounter which is the day of blood collection for 6-month HbA1c and lipid profile testing.

3.11 PLAN FOR DATA MANAGEMENT

3.11.1 STATISTICAL ANALYSIS

Data will be analysed using the Statistical Package for Social Sciences (SPSS) Version 26 (SPSS Inc, Chicago, IL, USA) software program. Categorical variables will be displayed using frequencies and percentages. Continuous variables will be presented as means and standard deviations. Chi-square test of independence and student's t-test will be used to examine the association between any 2 categorical variables and 2 continuous variables respectively.

The mean change in HbA1c after six months for all outcomes, will be calculated in both groups and the significance tested using the student's t-test for the mean difference between the intervention and control arm.

Statistical significance for all tests will be set at the 0.05 level, and all analysis will be 2-tailed.

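### The plan names Student's t-test without an unequal-variance version; naming Welch's test protects the 5% error rate if arm sizes and SDs both differ, at almost no cost

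*Combined protocol and SAP*

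**What the plan says.** Section 3.11.1 of the combined protocol and SAP compares the arms on mean change, with "the significance tested using the student's t-test for the mean difference between the intervention and control arm". The abstract repeats this. The sentence is written around HbA1c but refers to all outcomes, so it appears meant for the secondary continuous outcomes too. On level and sidedness: "Statistical significance for all tests will be set at the 0.05 level, and all analysis will be 2-tailed". On software: "Data will be analysed using the Statistical Package for Social Sciences (SPSS) Version 26". Nothing states whether the variances are pooled, and there is no mention of Welch's version, a variance check or a fallback.

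Three other statements bear on the point:

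- Section 3.2 sizes the trial with one common SD for both arms: "standard deviation of the outcome of interest which is 2.25".
- Section 3.2 allows for loss to follow-up: "An assumed 15% attrition and drop-out rate over the study period will be added". This is a single overall rate, not given by arm.
- Section 3.8 describes allocation: "randomise them equally into two groups based on computer-generated random numbers". Blocking is not mentioned.

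**The concern.** Student's two-sample test estimates one variance from both arms together. That is harmless if the arms are equal in size, or if the SDs are equal. When both differ, the pooled standard error is too small if the smaller arm has the larger SD (too many false positives), and too large if the larger arm has the larger SD (lost power and over-wide intervals).

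Both conditions could arise here. Loss over six months may not fall evenly, and the education arm has more contact (section 3.7.2) than usual care (section 3.7.1). Individualised education, given to patients with an HbA1c floor but no ceiling at entry (section 2.6), may change the spread of the change scores in one arm only. The p-value and confidence interval for the primary outcome would then be slightly off. There is also a practical matter: SPSS prints a pooled and an unequal-variance line side by side, and the text does not explicitly say which will be reported.

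**Working it through.** **The plan's own figure.** With the effect size of 0.7 from section 3.2, n per arm = 2 × ((1.960 + 0.842)/0.7)² = 32.04, stated as 32. Then 64 × 1.15 = 73.6, stated as 74, or 37 per arm. The figure reproduces. A loss of 15% from 74 leaves 74 × 0.85 = 62.9, so about 63 analysed.

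**Inputs.** From the documents: two-sided 5%, 1:1 allocation, 74 randomised, 15% loss, difference 1.5, SD 2.25. Assumed: the SD ratio between arms (1.5, that is 1.5 against 2.25; wider range 1.0 to 2.0), the split of completers, and normally distributed changes.

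**Formulae.** The squared standard error that Student's test estimates on average is

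[((n1 − 1)s1² + (n2 − 1)s2²)/(n1 + n2 − 2)] × (1/n1 + 1/n2),

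whereas the true value is s1²/n1 + s2²/n2. Welch's test estimates the true form and adjusts the degrees of freedom.

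**Worked case, 36 and 28 analysed.**

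- Larger SD in the smaller arm: the pooled variance is (35 × 2.25 + 27 × 5.0625)/62 = 3.475; times (1/36 + 1/28) = 0.06349 gives 0.2206. The true value is 2.25/36 + 5.0625/28 = 0.2433. The standard error is too small by a factor √(0.2206/0.2433) = 0.952, and 2Φ(−1.96 × 0.952) is about 6.2%.
- Larger SD in the larger arm: the pooled variance is (35 × 5.0625 + 27 × 2.25)/62 = 3.838, giving 0.2437 against a true 5.0625/36 + 2.25/28 = 0.2210. The factor is 1.050 and the error about 4.0%.

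**Simulation under no effect, SD ratio 1.5.** Separate runs agree to about 0.1 percentage point.

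| Analysed arms | Implied loss from 37:37 | Student, larger SD in larger arm | Student, larger SD in smaller arm | Welch |
|---|---|---|---|---|
| 32/32 | 14% and 14% | about 5% | about 5% | 5.0% |
| 34/29 | 8% and 22% | 4.3% | 5.8% | 5.0% |
| 36/28 | 3% and 24% | 4.0% | 6.3% | 5.0% |
| 37/26 | 0% and 30% | 3.7% | 6.7% | 5.0% |

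Unequal arms with equal SDs leave Student's test at 5.0%. Equal arms keep it between 5.0% and 5.2% even at an SD ratio of 2. At that ratio, with the larger SD in the smaller arm, 34/29 gives 6.3% and 37/26 gives 7.9%.

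**Cost of Welch when the SDs are equal** (difference 1.5, SD 2.25), power for Student against Welch: 74.65% and 74.61% at 32/32; 73.55% and 73.43% at 35/28; 72.77% and 72.54% at 37/26. The largest loss is about 0.2 percentage points. (Power is below 80% in these cases because 1.5/2.25 is 0.667, not 0.7. That is a separate matter.)

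**The case against.** The strongest reply is that the design is 1:1, the documents give one SD and one loss rate, and at equal arms both tests are at about 5%. The wider splits need strongly one-sided loss, for which there is no documented expectation. Usual-care patients also receive reminder calls for their data-collection visits. If loss really were 0% against 30%, bias from who was lost would matter more than a 1.7-point error in test size, and Welch's test does nothing about that. Pooling is inferred from the test's name. All of this stands, and it limits the point to a minor one.

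Three stronger readings are tempting and are not supported.

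- *The error probably runs towards false positives.* One might expect a smaller and more variable control arm. But the outcome is change. If education lowers high values more, follow-up values narrow while change scores widen. Take follow-up = slope × baseline + noise, so that the variance of change is (1 − slope)² × baseline variance + noise variance. With an assumed baseline SD of 2.0 and noise SD of 1.5, moving the slope from 0.8 to 0.4 raises the SD of change from √(0.04 × 4 + 2.25) = 1.55 to √(0.36 × 4 + 2.25) = 1.92. The larger SD then sits in the education arm. If that arm is also the better retained, Student's test is conservative, at about 4.4% with 36/28.
- *Randomisation will make the arms unequal.* With unrestricted random numbers, 74 patients split 37:37 only 9% of the time, and one arm starts below 32 in 20% of cases. But section 3.8 speaks of equal randomisation and does not say that allocation is unrestricted.
- *The planned test is wrong as it stands.* Its error rate departs from 5% only if sizes and SDs both differ, and neither difference is documented.

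**Conclusion.** The point holds as a minor, essentially free improvement, not as a demonstrated error or a threat to the primary result. At an assumed SD ratio of 1.5, the error of the pooled test lies between about 4.3% and 5.8% for a moderate imbalance and between 3.7% and 6.7% at a pessimistic one. It reaches nearly 8% only with an SD ratio of 2 and all losses in one arm. The sign of the departure cannot be known in advance, which is the reason to choose a test that holds 5% either way. The figures rest on normal changes and on assumed SD ratios and completer splits. They were worked for HbA1c; no SDs are given for FBG, blood pressure, weight or LDL-C, so no outcome-specific size can be stated for those.

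**What to change.** In section 3.11.1 and in the analysis paragraph of the abstract, replace *student's t-test* with *Welch's unequal-variance t-test* for between-arm comparisons of continuous outcomes, and state that the mean difference will be reported with the 95% confidence interval from the same test. Make the change before outcome data are seen, so that the choice between the two SPSS lines is fixed in advance.

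The cost is one phrase in two places and at most about 0.2 percentage points of power if the SDs prove equal. The sample size, data collection and software are unchanged.

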ANALYSIS: Data will be analysed using the Statistical Package for Social Sciences (SPSS) Version 26 (SPSS Inc, Chicago, IL, USA) software program. Categorical variables will be displayed using frequencies and percentages. Continuous variables will be presented as means and standard deviations. Chi-square test of independence and student's t-test will be used to examine the association between any 2 categorical variables and 2 continuous variables respectively. The mean change in HbA1c after six months for all outcomes, will be calculated in both groups and the significance tested using the student's t-test for the mean difference between the intervention and control arm. Statistical significance for all tests will be set at the 0.05 level, and all analysis will be 2-tailed.

EXPECTED OUTCOME: Our study will evaluate the effectiveness of DSME in improving glycaemic control using a mixed delivery strategy. If DSME is shown to be effective it will enhance scaling up of this intervention in diabetes clinics and the adoption of this model in the

Version 1 30 May 2023

national diabetes management guidelines. This will lead to improved knowledge of diabetes, glycaemic control, reduced lost hours due to hospitalization from poorly controlled diabetes mellitus and improved patient outcomes.

BACKGROUND INFORMATION

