2.5 OUTCOMES

2.5.1 PRIMARY OUTCOME

Mean change in HbA1c at 6 months

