2.5.2 SECONDARY OUTCOMES

- 1) Mean change in FBG at 3 months
- 2) Mean change in blood pressure at 6 months
- 3) Mean change in body weight at 6 months
- 4) Mean change in LDL-C at 6 months

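### The primary HbA1c analysis ignores baseline HbA1c, which every participant has; adjusting for it costs almost nothing and usually gives a more precise estimate

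*Combined protocol and SAP*

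**What the plan says.** - **Primary outcome (2.5.1):** "Mean change in HbA1c at 6 months".
- **Analysis (abstract and 3.11.1):** "The mean change in HbA1c after six months for all outcomes, will be calculated in both groups", then tested with a Student's "t-test for the mean difference between the intervention and control arm". Neither place names a covariate, regression model or other baseline adjustment.
- **Baseline HbA1c:** under 3.6, people who pass screening and consent "will have blood sample collected for measurement of baseline HbA1c", and only those above 7.9% are enrolled (also 2.6 and 3.10.1). Sections 3.9.3 and 3.10 (Follow up) provide the 6-month value.
- **Allocation (3.8):** the investigator will "randomise them equally into two groups based on computer-generated random numbers". No stratification or other control of baseline HbA1c is described.
- **Sample size (3.2):** a difference of 1.5 points, "standard deviation of the outcome of interest which is 2.25", and "An assumed 15% attrition and drop-out rate over the study period", giving 74 in total. The section does not say whether 2.25 is the SD of HbA1c or of its change, and gives no correlation between visits.
- **Secondary outcomes (2.5.2):** also mean changes, for example "Mean change in FBG at 3 months".

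**The concern.** A change score subtracts the whole baseline value, which is optimal only if 6-month HbA1c rises by exactly one point per point of baseline within each arm. Regression to the mean usually makes that slope less than 1, and the change score then carries avoidable noise from baseline. ANCOVA estimates the slope instead of fixing it at 1.

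This matters more in a small trial. About 31 participants per arm are expected to be evaluable, and nothing in the allocation prevents a chance gap in baseline HbA1c. If such a gap appears, an adjustment chosen afterwards is open to challenge; one specified beforehand is not.

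**Working it through.** **1. The plan's own figure.** n per arm = 2 × ((1.960 + 0.842)/ES)². With the stated ES of 0.7 this is 32.04, reported as 32; 64 × 1.15 = 73.6, reported as 74. (The unrounded ES, 1.5/2.25 = 0.667, gives 35.3, so 36. That is a separate issue.) Evaluable after 15% loss: 74 × 0.85 / 2 = 31.45, taken as 31 per arm.

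**2. Same target.** With baseline in the model, the arm coefficient is identical whether the outcome is 6-month HbA1c or change, so section 2.5.1 can stay as written. Under 1:1 randomisation it estimates the same mean difference as the t-test.

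**3. Variance ratio.** Let b be the within-arm slope of 6-month on baseline HbA1c, s the baseline SD among those enrolled, and V the residual variance.

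- Change score: (1 − b)²s² + V
- ANCOVA: V, times about 1 + 1/(62 − 4) = 1 + 1/58 for estimating the slope

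Before that cost the ratio V / ((1 − b)²s² + V) cannot exceed 1, and equals 1 only when b = 1.

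**4. Inputs not in the documents (assumed).** Screened HbA1c is normal with mean 9.5 and SD 2.25 at both visits, cut at 7.9. The cut lies at a = (7.9 − 9.5)/2.25 = −0.711; λ = φ(a)/(1 − Φ(a)) = 0.407; s = 2.25 × √(1 + aλ − λ²) = 1.66. V = 2.25²(1 − b²). The correlation among enrolled participants is r = sb/√(s²b² + V), solved for b at each r.

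| r | b | SD of change | ANCOVA residual SD | Ratio | Ratio after slope cost | 31 / ratio after cost |
|---|---|---|---|---|---|---|
| 0.3 | 0.392 | 2.30 | 2.07 | 0.808 | 0.822 | 37.7 |
| 0.5 | 0.616 | 1.88 | 1.77 | 0.885 | 0.901 | 34.4 |
| 0.7 | 0.799 | 1.39 | 1.35 | 0.943 | 0.959 | 32.3 |
| 0.9 | 0.942 | 0.76 | 0.76 | 0.984 | 1.001 | 31.0 |

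**5. Sensitivity to the assumed population** (ratio after slope cost, r = 0.3 / 0.5 / 0.7 / 0.9):

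- Screened mean 8.2 (s = 1.41): 0.89 / 0.95 / 0.98 / 1.01
- Screened mean 10.5: 0.77 / 0.86 / 0.93 / 0.99
- Equal SDs at both visits among those enrolled: (1 + r)/2 = 0.65 / 0.75 / 0.85 / 0.95, or 0.66 / 0.76 / 0.86 / 0.97 after the cost

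**6. Power for 1.5 points** (noncentral t, 31 per arm; 60 df for the t-test, 59 for ANCOVA; step 4 ratios):

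| r | 2.25 is SD of change: t-test | ANCOVA | 2.25 is SD of level: t-test | ANCOVA |
|---|---|---|---|---|
| 0.3 | 73% | 81% | 71% | 79% |
| 0.5 | 73% | 78% | 87% | 90% |
| 0.7 | 73% | 75% | 99% | 99% |
| 0.9 | 73% | 73% | >99% | >99% |

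If 2.25 is the SD of change, the 95% CI half-width is 1.14 points for the t-test and 1.04 / 1.09 / 1.12 / 1.14 for ANCOVA. Worst case, slope exactly 1: half-width 1.143 to 1.153, power 73.3% to 72.6%. In simulation (20,000 replicates per case) power agreed to within about one percentage point, and type I error was 4.8 to 5.2% for both methods.

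**7. Chance imbalance.** The difference in baseline means has SE 1.66 × √(2/31) = 0.42, so a gap above 0.5 points has probability about 24% (16% with s = 1.41). A 0.5-point gap moves the unadjusted change estimate by (1 − b) × 0.5 = 0.30 / 0.19 / 0.10 / 0.03 points.

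**The case against.** The strongest reply is that nothing here is an error. The t-test is valid, tests the outcome defined in 2.5.1, and is the two-mean comparison that 3.2 sized. That is true, and no bias is alleged.

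The second reply is that the benefit may be small. No passage supports a value of r, and at r of 0.7 or more the gain is about one patient per arm or none. A screened mean of 9.5 with SD 2.25 also puts 87% above 7%, whereas the introduction and the relevance section say about 70% of patients in Ghana are poorly controlled. With SD 2.25, 70% above 7% implies a mean near 8.2, where the gain is about 4 / 2 / 0.5 / 0 patients per arm. That figure is national and a tertiary clinic may differ, but it is the only anchor in the documents and deserves weight.

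Third, the SD-of-change column in step 6 applies ratios derived with a level SD of 2.25 to a change SD of 2.25. The two coincide only near r = 0.3. Making the model consistent moves ANCOVA power at r = 0.7 from 75.1% to 74.5%, and at r = 0.9 needs an implausible screened SD of about 7.5. The figures show scale; they are not forecasts.

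Fourth, the extension to secondary outcomes has less support. Section 3.9.3 gives baseline lipid sampling and fasting glucose at every hospital visit, but 3.9.2 does not time the blood pressure and weight measurements. Their baselines are only implied by the outcomes being changes.

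These points limit the size and scope of the benefit. None argues for leaving baseline HbA1c unused.

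**Conclusion.** The concern holds, as a nearly free improvement and not as a flaw in validity. The direction is secure: same target, large-sample variance never larger, and at worst about 2% of variance lost (0.7 percentage points of power in the case worked). The size is not. Across the normal populations assumed above, ANCOVA saves roughly 11 to 23% of variance at r = 0.3 and between nothing and about 7% at r = 0.7 to 0.9; equal SDs among those enrolled would give more. These figures rest on an assumed population, 31 evaluable per arm and assumed correlations. Adjustment does not replace correcting the sample-size calculation.

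**What to change.** In section 3.11.1 and the abstract, make the primary analysis a linear model with 6-month HbA1c as outcome, arm as factor and baseline HbA1c as covariate. Report the adjusted mean difference with its 95% CI, and keep the t-test on change as a sensitivity analysis. State in 3.2 whether 2.25 is the SD of change or of level.

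Use the same model for the secondary outcomes, each with its own baseline and at its own time point (3 months for fasting glucose, 6 months for the others), after stating in 3.9.2 when baseline blood pressure and weight are taken.

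The cost is a paragraph of text and one degree of freedom. HbA1c needs no new samples or visits, and SPSS, the planned software, fits the model. The change should be made before outcome data are examined.
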